The maintenance exercise group is a commissioned exercise group post pulmonary rehabilitation. Patients are invited to join a class to ensure they continue to exercise at a prescribed level. This group also provides valued social contact. Continued exercise is vital to ensure physical wellbeing but might be continued outside a clinical setting in a way, which also enhances social contact to replace the social role that the maintenance exercise group currently holds for COPD patients. The current clinical contact time could be replaced by voluntary groups and other exercise providers including informal contacts linked into personal networks of support which might ensure an equivalent or enhanced supportive social environment which is less reliant on existing health care services.

The supportive self-management tool GENIE (Generating Engagement in Network Involvement) has been implemented effectively in a 'My LIFE a Full life' (MLAFL), project, based on the Isle of Wight, (Kennedy et al 2016). The MLAFL programme focuses on people with long-term conditions, older people and those with mental health needs, with three priority areas identified:

- Self-Care and Self-Management
- Crisis Response
- Locality Working

The GENIE implementation purposefully sampled people with type 2 diabetes in order to represent the long-term conditions group. Diabetes is a long term life limiting condition, with episodes of acute illness- during hypo/hyper-glycemic events. However COPD is different to diabetes because of limitations caused by breathlessness which can be physically disabling and socially isolating. Therefore implementing and evaluating this already successful social mapping tool into the COPD service is valuable to understand:

- Differences and similarities in its utility for different Long term conditions
- Barriers to social activity including those linked to a person's physical condition
- Response, uptake and practical benefits of GENIE for COPD patients
- Capacity of voluntary, community and personal network to take on the work previously undertaken in the maintenance clinic.
- Health economic and service utilisation benefits
- Exploration of weak or fractured social networks in COPD

Purpose

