The main aim here is to increase long term health care management options in Solent NHS Trust by building social capacity to support self-management. The GENIE tool will be introduced into the COPD service to improve options for social groups and exercise when leaving a pulmonary rehabilitation group, or when clinically unable to participate in exercise.

- to build social networking awareness and the importance of utilising existing social resources in the professional and voluntary members of the COPD service,
- to use social network mapping techniques and preference elicitation to engage COPD patients in reflecting on their support preferences and needs, help them access further resources and knowledge
- Evaluate the success of the social mapping techniques (GENIE) in the COPD patient population
- Evaluate the cost benefit to both to patients and to the health service of the GENIE in the COPD patient population

Objectives

Primary objectives

Compare and evaluate the health care utilisation and quality of life (burden of disease) in COPD patients using GENIE alongside usual care after leaving the COPD service with those offered only a current practice discharge plan.

Secondary objectives

Compare and evaluate the change in health behaviours, in particular diet and lifestyle in COPD patients using GENIE alongside usual care after leaving the COPD service with those offered only a current practice discharge plan.

Observe and understand the uptake and utilisation of the GENIE recommendations by COPD patients.

Explore social complexities in the COPD population.

Implementation Design

[figure not shown]
This protocol is concerned with the implementation and evaluation of the GENIE tool in the community facilitated by the COPD team and the subsequent evaluation of the GENIE in direct comparison to usual clinical practice.

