Selection and patient information: Patients in the COPD service; at the outset of their assessment, the end of PR and during maintenance sessions will be informed that the GENIE implementation evaluation is in progress.

Patients participating in these aspects of the service will be offered the opportunity to volunteer for the study, by the clinical team. If patients are interested they can then provide their names to the clinical staff to keep on a secure Solent database. Patient information sheets and invitation letters will be given out to the interested patients at their clinical visits to minimise postal and /or extra visits.

Once patients have received an information sheet, they will be allowed at least 72 hours to read and digest the information, (patient information sheets, consent and GP letters are separate documents), and share this with their friends and family if they wish to. Ideally, patients are provided with information in their clinical visits and are returning for clinical visits then appointments for research could be amalgamated with usual clinical visits. In this way extra study visits can be reduced. Patients, now participants, will be invited to consent and be randomised at the point of leaving usual clinical care. Furthermore, all patients at this point will have the opportunity to opt out of the study.

Once the participant is randomised (using block randomisation technique in clinic), then they will all receive normal clinical care (discharge planning with suggested activities), and the GENIE tool intervention, in the GENIE group, this is in addition to usual clinical care. Baseline questionnaires will also be administered at this visit.

The follow up period will commence 3 months (12 weeks) (+/- 1 week) from the day the GENIE tool was initially delivered. Participants will be invited back, via letter and /or phone call to attend their three month follow up visit at Bitterne Health Centre.

Solent NHS Trust will be the overall NHS organisation with one venue for study delivery; Bitterne Health Centre.

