Block randomisation technique, a commonly used technique in clinical trial design to reduce bias and achieve balance in the allocation of participants to treatment arms, especially in this case when the sample size is small (Efird, J. 2010). In order to reduce unconscious bias of the researcher, pre-prepared envelopes containing the possible combinations of group allocation, will be stored in a locked drawer in Bitterne Health Centre. The intention is to randomize in blocks of four, as this will complement the clinic structure. Therefore, each envelope will contain a pre-determined allocation pattern for that clinic (AABB, ABAB, BABA etc.).

The researcher team will share an excel spread sheet which will be set to generate a random number sequence. The next sequential number will be selected, which will then correspond to an envelope with the predetermined sequence. In this way the envelope selection is random, then sequence in the envelopes is also random, but ensures 50/50 grouping of participants. Baseline data for descriptive statistics will also be collected. (Data capture form appended)

In order to conduct meaningful analysis recruitment needs to reach at least 30 patients, in each group, however the maximum could be 60 in each group, 120 patients in total. Therefore recruitment could take between 6-9 months. The timeframe can be increased if necessary.

Initial / Baseline data collection:

Socio-economic data will be collected including; disease severity (FEV1), gender, EQ-5D, health care utilisation questionnaire, HEIQ and wellbeing questionnaires (CAT, GAD, PHQ-9), as well as an optional health behaviour questionnaire, from both the usual care group and the interventional group. Please note CAT, GAD, PHQ-9 FEV1 and gender are already captured routinely during clinical consultation.

Intervention

[figure not shown]
Assessment stratification and feedback:

Stage 1: The patient will complete a questionnaire online with the researcher/clinician. The patients will be asked to name the important people and activities in their network, type of relationship and frequency of contact using the concentric circles diagram.

Stage 2: The online process: consisting of series of questions will be used to elicit the participant's values and preferences for activities and support resources.

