Stage 3: This section will then link individuals to prioritised and valued activities and resources (links are to a pre-created database where local organisations and resources have been categorised).

Stage 4: The GENIE Tool then presents options in a user-friendly way, on a Google map with clear details about access, an example below:

Both groups will receive usual care, however one arm will have the addition of the intervention both will be called for a review at:

Three monthly follow up (+/- 1 week)

Six questionnaires will be administered. EQ-5D, health utilisation questionnaire, HEIQ and wellbeing questionnaires (CAT, GAD, PHQ-9), as well as the optional health behaviour questionnaire, so in 30 participants this will be seven, these will be repeated at 3 months post intervention (+/- 2 week). Furthermore, for those in the intervention arm, feedback and reflection discussions will be initiated using the network diagrams. Participants will be asked again for their permission to tape record these discussions to ensure parity and quality assurance between researchers.

Analysis of Outcomes

The study gathers data from the intervention arm and the non-intervention arm at baseline and 3 months post intervention. Results will be compared between the groups at baseline and 3 months post intervention. An economic analysis will be performed using a modified version of the Client Service Receipt Inventory (CSRI) (Beecham and Knapp 1999) Medication, health service use will be measured at baseline, 3 months post implementation and follow up. The modified version has been tailored to capture the needs of the target population (COPD patients). The CSRI has been widely used in previous research studies and has been evidenced as a valid measure of frequency of health service use (Patel 2005). The EQ5D is included to assess health status of patients during the GENIE intervention. Wellbeing score (CAT) and HEIQ and in the optional sub-group health behaviours (dietary intake, appetite, alcohol consumption and smoking habits) will be compared at baseline and 3 months. Furthermore, patient uptake of the social activities is to be recorded on paper using the Genie tool and compared between groups.

Rationale for the service implementation and evaluation design

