GENIE is a way to help people think about the links they have with others to manage a health problem (local groups, friends, acquaintances, family members, professionals) and to reflect on their involvement in health and wellness activities and their ability to live an ordinary life with a long term condition. By using GENIE and thinking or talking through the GENIE mapping tool, individuals can visualize their network and can reflect on connections that provide value and resources for managing and where there are gaps in support- this might be social, practical or emotional as well as specifically related to a health condition.

Cost of the intervention

The service lead has already secured some funded time to enable the GENIE library build the initial database and to deliver the initial implementation research project into the service.

Training on building the COPD sections of the database update in Dec 2016: - following this access to the website <https://genie.soton.ac.uk/> and the ability to create a database of local organisations that is accessed by the website.

Initial overview session has taken place in a COPD team meeting on the Thursday 14th April 2016.

Training Pre Month 0

Training will be delivered by the self-directed support for self-management team who developed the GENIE intervention. The session will take place over an afternoon.

The GENIE approach consists of three elements

- Personal network mapping
- Identification of needs and personal interests
- Linking to local resources using website and tailoring to needs and interests through facilitation.

1. Personal network mapping using concentric circle tool

This involves, constructing and visualising a personal network of members and contact supporting long term condition management, four types usually emerge from this process (restricted, family, friend, diverse).

2. Identification of needs and personal interests by working through preference questions.

- Key questions centred on well-being and social needs and preferences
- Working with personal preferences and need to articulate a set of personal goals

- Link to potential sources of support in community settings through connecting with a dedicated resource.
- In order to maintain privacy, pseudonyms will be used on the website and the printed preferences stored in a locked drawer in Solent NHS space (including pseudonyms of friends and relatives)

3. Feedback and example

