Following the training, the participants will be given the tools required to roll out the intervention

- Paper and web-based concentric circles with typologies and support suggestions
- Guidebook on how to deliver GENIE
- Access to the database and website

Identification, enrolment and randomisation

[figure not shown]

Table of Events

	Consent and Randomisation	Pre – intervention data collection	12 weeks post intervention data collection (+/- 1 week)	Potential 1 year follow up phase
Consent form discussion and taking informed consent	x			
Randomisation (Block)	x			
EQ-5D		X	x	x
Health Care Utilisation Questionnaire		X	x	x
Socio-economic background / demographic data		X		
Gender		X		
Disease severity (FEV1)		X		
HEIQ (Self-management)		X	x	
Optional Health behaviour questionnaire		x	x	x
CAT		X	x	x
Gad-7 /		X	x	
PHQ-9		x	x	x
Uptake discussion / online survey			x	x

Quality Assurance

The delivery of the intervention will be taped in as many cases as consented to ensure that the intervention is delivered consistently by the research team to all patients. The tape recording is for quality assurance, and is not intended for research utilisation or publication.

Future work

The participants included in this initial 3 months of the study could be followed up again in 1 year (12 months) to ascertain longer term outcomes and longevity of connections made. This element could consist of a paper or online survey to understand the uptake rates of the social actives 1 year on, and further investigation into QOL, **healthcare use and the option of assessing health behaviours.** All participants would be given the option of continuing for a year, and therefore those who continue would be decided by participant preference to remain in the study.

Analysis Plan

Primary Outcomes

Descriptive statistics of the cohort,

Descriptive statistics of the cohort will be reported including but not limited to; age, gender, severity of disease then the analysis will be broken down into 5 distinct sections;

- a) Pre and post intervention cost utility analysis for the usual care group and the intervention group.
- b) Comparative group - pre and post cost utility analysis; calculated cost per QALY (quality adjusted life years) gained and cost of healthcare usage per patient– usual care group at 3 months after leaving the COPD service compared with the post intervention group 3 (+/- 1 week) months after leaving the COPD service, with significance.

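### The economic plan has no stated means of measuring GENIE delivery cost or maintenance-class use, so incremental cost could be misstated in either direction

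*Combined protocol and SAP*

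**What the plan says.** Cost effectiveness is in the study title, and the Purpose section sets the aim to "Evaluate the cost benefit to both to patients and to the health service of the GENIE" tool in COPD patients. Under Analysis Plan, Primary Outcomes, items a and b are cost-utility analyses. Item b compares the groups at 3 months on "calculated cost per QALY (quality adjusted life years) gained and cost of healthcare usage per patient".

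On cost inputs, Analysis of Outcomes says "An economic analysis will be performed using a modified version of the Client Service Receipt Inventory (CSRI" and continues: "Medication, health service use will be measured at baseline, 3 months post implementation and follow up". No other source of costs is named.

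GENIE is given to one arm only. Under Selection and patient information, both groups receive normal care and, for the tool, "in the GENIE group, this is in addition to usual clinical care". It needs staff: Stage 1 of the Intervention section says "The patient will complete a questionnaire online with the researcher/clinician", and the intervention arm also has a network discussion at the 3-month visit.

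The section headed Cost of the intervention says "The service lead has already secured some funded time to enable the GENIE library build the initial database" and to deliver the initial project, then describes an afternoon of training. It gives no sum, no unit cost and no instruction on whether these items are charged to the GENIE arm.

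On the service GENIE might displace, the Background says of the maintenance exercise group: "The current clinical contact time could be replaced by voluntary groups and other exercise providers".

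**The concern.** A cost-utility comparison needs every resource that may differ between arms. Two are at issue here. GENIE delivery (facilitator time, training, database build and upkeep) falls on the intervention arm alone. Maintenance-class attendance may fall in that arm if community activities take the class's place. If neither is collected, the cost difference behind the cost per QALY lacks the price of the intervention and one of its main hoped-for savings.

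The result is meant to be used. Ethical Considerations says the trial should show the benefits in time and cost before full-scale implementation, and Risks / benefits says GENIE will be offered to all patients if a benefit is seen. The cost of delivering it bears directly on that decision.

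**Working it through.** **Step 1: is either cost captured?** The documents give no unit cost, cost per QALY, QALY gain or threshold, so there is no economic figure to reproduce. The first check is textual.

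| Resource | Healthcare Usage Questionnaire | Table of Events | Cost of the intervention section |
|---|---|---|---|
| Facilitator time, GENIE session | No line | No row | No amount or rule |
| Facilitator time, 3-month discussion | No line | Uptake discussion listed, time not recorded | Not mentioned |
| Training | No line | No row | One afternoon, no cost |
| Database build and upkeep | No line | No row | Some funded time, no cost |
| Maintenance class | No line | No row | Not mentioned |

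The free-text row for other services could pick up a GENIE contact or a class only by chance. The item on other patient-borne costs covers such things as gym membership, not delivery of the tool.

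**Step 2: direction.** Let g be the GENIE delivery cost per participant, and m the maintenance-class cost per participant in usual care minus that in the GENIE arm.

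- True incremental cost = measured incremental cost + g − m.
- Understatement of incremental cost = g − m.

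With g assumed at £50:

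| m (assumed) | g − m | Effect of the omission |
|---|---|---|
| £0 | +£50 | favours GENIE |
| £50 | £0 | cancels |
| £100 | −£50 | works against GENIE |

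The documents give neither g nor m, so the sign is open.

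**Step 3: sensitivity of cost per QALY to g alone (m = 0).** For a positive QALY gain:

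- QALY gain = EQ-5D gain × 0.25 year × f, with f = 0.5 if the gain builds up linearly and f = 1 if it is immediate.
- Shift in cost per QALY = g ÷ QALY gain.

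Worked case: 0.05 × 0.25 × 0.5 = 0.00625 QALY, and £50 ÷ 0.00625 = £8,000 per QALY.

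| EQ-5D gain (assumed) | QALY gain, linear | g = £25 | £50 | £100 | £200 |
|---|---|---|---|---|---|
| 0.02 | 0.0025 | £10,000 | £20,000 | £40,000 | £80,000 |
| 0.05 | 0.00625 | £4,000 | £8,000 | £16,000 | £32,000 |
| 0.10 | 0.0125 | £2,000 | £4,000 | £8,000 | £16,000 |

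An immediate effect halves every entry, so the whole assumed grid runs from £1,000 to £80,000. If the QALY gain is zero or negative, this shift in the ratio does not apply, but incremental cost is still wrong by g − m.

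**Step 4: set-up cost.** The plan allows 30 to 60 participants per group. A fixed set-up sum S shared over the GENIE arm is S/30 or S/60 per participant, a twofold difference from recruitment alone. The method of apportionment therefore has to be stated.

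**The case against.** A reader might infer that the plan excludes GENIE delivery cost and that cost per QALY is therefore biased in favour of GENIE. The documents do not support this, for two reasons.

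- **The plan is silent and states no exclusion.** It says the analysis uses the modified inventory, not that nothing else will be used. It has a section on the cost of the intervention, and item b lists cost per QALY separately from healthcare usage cost. The questionnaire may not be the only source: medication is to be measured, yet the appended form has no medication item, so either another source exists or the form is incomplete. A data capture form is also said to be appended but is not in the text available to me. It is mentioned in connection with baseline descriptive data.
- **The net direction is not established.** The same questionnaire misses maintenance-class use, and a saving there would work against GENIE. Nor does class use differ between arms by design: both receive usual care, and replacement of the class is a hypothesis.

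It can also be said that the costs are recoverable afterwards. That is partly right. Training is one afternoon, database effort could be estimated, and class attendance could be extracted if the service keeps records, though the documents mention none. Session time per participant would be less precise in retrospect. Tape recordings are made only with consent and are reserved for quality assurance.

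Finally, whether training and database build belong in the cost depends on the perspective taken, which the plan does not state. That supports reporting both ways.

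None of this supplies a source for either cost or a rule for including it. The gap stands.

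**Conclusion.** The point holds as a gap in data collection and in the analysis rule. The primary cost-per-QALY comparison has no stated means of including a cost that falls only on the GENIE arm, or the use of a service that GENIE may partly replace. If only the named inputs are used, incremental cost is wrong by g − m per participant, and the sign cannot be determined from the documents.

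The size cannot be determined either. The pound figures rest wholly on assumed delivery costs and EQ-5D gains, and the cost-per-QALY shifts also assume a positive QALY gain and m = 0. They show only that, over a 3-month horizon, a modest omitted cost could move cost per QALY by thousands of pounds. This should be corrected, but it does not touch the randomisation, the sample size or the clinical outcomes.

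**What to change.** 1. Log facilitator time for each GENIE session and each 3-month network discussion, with staff grade, and add the resulting delivery cost to the GENIE arm in items a and b of the Analysis Plan.
2. Report results with and without training and database set-up cost, and state how these and database upkeep are apportioned (over trial participants or over expected users).
3. Add one questionnaire line for maintenance-class attendance, asked of both arms at both time points, or use attendance records if the service holds them.
4. State the perspective and the source of unit costs.

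The cost is a short time log, one extra form line or a records extract, and a little more analysis and wording. The cost per QALY may become less favourable to GENIE once delivery is charged; any reduction in class use would offset that.

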(English) EQ-5D-5L Pdf

Health care utilisation questionnaire

Healthcare Usage Questionnaire

We would like to know how much use you have made of the health and social services over the last 3 months. If you are not exactly sure, we would rather have your best guess than no information at all.

Please answer every question, even if the answer is 'No'.

1) Over the last 3 months, if, and how many times, have you used any of the following:

Type of Service	No	Yes	If yes: Number of visits
GP		At home	
		In the surgery	
		On the phone	
Practice nurse		At home	
		In the surgery	
		On the phone	
Social worker		At home	
		In the facility	
		On the phone	
Visit at home from a community nurse or Dr			
Specialist community clinic –with consultant			
NHS Smoking Cessation clinic			
Other (describe)			

2) Hospital outpatient visit for breathing related issues

Episode*	Name of the hospital	Reason for appointment	Specialty of Department	Number of appointment*
1 st				
2 nd				
3 rd				
4 th				

*Episode means a visit or group of visits related to a particular problem. Please write down how many appointments you have had for each episode

3) Accident and Emergency for COPD / breathing issues

Episode	Name of the hospital	Reason for visit	Referral from
1 st			GP
			Outpatient
			Self-referral
2 nd			GP
			Outpatient
			Self-referral
3 rd			GP
			Outpatient
			Self-referral
4 th			GP
			Outpatient
			Self-referral

4) Hospital Inpatient for COPD / breathing and chest issues

Episode	Name of hospital	Ward Speciality	Reason for admission	No of nights*
1 st				
2 nd				
3 rd				
4 th				

*If you were treated as a day patient (day case), then please write 0 under "number of night"

5) Are you currently in paid employment?

No (please go to question 5b) Yes (please go to question 5a)

5a If yes, how many days have you been absent from work because of COPD in the last 3 months?
Please state how many days 5b If you are not employed:,

In the last 3 months have you had to stop work completely due to your COPD disease

No

Yes

6) Over the last 3 months has a relative or friend taken time off work to look after you?

No

Yes, how many days

7) In the last 3 months, approximately how much additional money have you spent on travel (taxi car park fees and public transportation because of your COPD disease)

None

Yes, I spent £ _____

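### Medication is promised as a measured input to the economic analysis, but no form shown and no named records source collects it

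*Combined protocol and SAP*

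**What the plan says.** Analysis of Outcomes names a modified CSRI as the instrument for the economic analysis and then states that "Medication, health service use will be measured at baseline, 3 months post implementation and follow up".

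The instruments appear in three places.

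- Initial / Baseline data collection lists the EQ-5D, a health care utilisation questionnaire, HEIQ, CAT, GAD and PHQ-9, with an optional health behaviour questionnaire.
- The section on the three-month follow-up repeats the set: "Six questionnaires will be administered. EQ-5D, health utilisation questionnaire, HEIQ and wellbeing questionnaires (CAT, GAD, PHQ-9"), again with the optional form.
- The Table of Events schedules the "Health Care Utilisation Questionnaire" before the intervention, at 12 weeks and at the potential 1-year follow-up.

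The Appendices reproduce that questionnaire. Its first question begins "Over the last 3 months, if, and how many times, have you used any of the following".

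Under Primary Outcomes, the Analysis Plan includes "Pre and post intervention cost utility analysis for the usual care group and the intervention group", and a comparison of the groups on "calculated cost per QALY (quality adjusted life years) gained and cost of healthcare usage per patient".

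**The concern.** A cost analysis can use only the resources that were recorded. The plan commits to measuring medication at each time point, yet the one resource-use form it shows has no question on it. Health care utilisation is part of the primary objective, and the cost results are listed under Primary Outcomes, so the gap is in a main analysis. The form relies on three-month recall, so medication use that is not asked about at the visit is hard to recover later unless records are used.

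A smaller version of the same problem concerns the maintenance exercise class. The Background describes it as a commissioned group whose clinical contact time might be taken over by voluntary groups and other providers. Implementation Design says that the COPD team delivers it and that patients leaving pulmonary rehabilitation are usually offered it. It is therefore a service that the intervention may displace, and a difference between arms is plausible. The usage questionnaire does not name it.

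**Working it through.** The documents give no figure to reproduce. The check sets the promise against each place where medication could be collected.

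**1. Instruments listed at three months.** EQ-5D, health utilisation, HEIQ, CAT, GAD and PHQ-9 make 6; the optional health behaviour form makes 7. Only 1 of the 7 is a resource-use form. The documents describe the others as covering health status (EQ-5D), self-management (HEIQ), wellbeing (CAT, GAD, PHQ-9) and, for the optional form, "health behaviours (dietary intake, appetite, alcohol consumption and smoking habits) will be compared at baseline and 3 months".

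**2. Healthcare Usage Questionnaire (Appendices).**

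| Questions | Content | Medication item |
|---|---|---|
| 1–4 | Service contacts: primary care and community, outpatient, A&E, inpatient | None |
| 5–6 | Employment, absence, time taken off by relatives or friends | None |
| 7–8 | Participant's own spending: travel, other costs | None |

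Total: 0 of 8. A participant might volunteer purchased medicines under question 8, but that question records personal spending and its examples do not include medicines.

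**3. Table of Events.** Of 13 rows, none is for medication, prescriptions or a separate CSRI. The usage questionnaire is the only resource-use row.

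**4. Data from routine care or records.** The baseline section names CAT, GAD, PHQ-9, FEV1 and gender as routinely captured. Medication is not among them, and no GP, prescribing or pharmacy record is named.

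**5. Data capture form.** The randomisation text says "Baseline data for descriptive statistics will also be collected. (Data capture form appended"). The form is not shown. It is described only for baseline descriptive data and is in neither the three-month list nor the Table of Events.

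**6. Effect on the results.** Write the mean cost per patient in arm j as C_j = S_j + M_j, where S_j is the cost of recorded services and M_j the cost of medication. With the forms shown, only S_j is observed.

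- Cost per patient in arm j is understated by M_j.
- The between-arm difference omits M_GENIE − M_usual. This is zero if the two are equal.
- The pre/post change within an arm omits M_post − M_pre. This is zero only if medication cost does not change over the period.
- Cost per QALY should be (ΔS + ΔM)/ΔQALY and would be reported as ΔS/ΔQALY. It is unaffected if ΔM = 0.

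The documents give no medication use and no unit costs, so none of these terms can be evaluated.

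**7. Maintenance class.** Question 1 names 6 service types: GP, practice nurse, social worker, home visit by a community nurse or doctor, consultant-led specialist community clinic, and smoking cessation clinic. The class is in 0 of the 6; only the free-text row for other services could hold it. One of the two recruitment groups in Implementation Design has been in maintenance for a year or more, so class contacts can fall within the baseline three-month recall period. How many fall after randomisation is not stated.

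**The case against.** *Most of the forms cannot be read.* Six of the seven three-month instruments are not reproduced, nor is the data capture form. This stands as a limit on confidence. It does not supply a route: the documents' own descriptions of the six do not mention medication, and the data capture form is tied to baseline, so three months and follow-up would remain uncovered even if it recorded medicines.

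*The modified CSRI may be a different form.* The protocol never says that the appended questionnaire is the modified CSRI. If it is not, the defect changes: the instrument named for the economic analysis is then absent from both questionnaire lists and from the Table of Events. Either way the text needs correcting.

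*Medication may be a stray word.* The Objectives and the Analysis Plan speak only of health care use and its cost, and which costs to include is partly a choice of perspective. This stands to the extent that removing medication from the stated costs is a legitimate repair.

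*Equal omitted costs cancel.* This is correct for the between-arm difference, and the documents give no reason to expect medication to differ by arm over 12 weeks. It does not complete the cost per patient reported for each arm, and equality cannot be checked if medication is not collected.

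*The class can already be written in.* This is also correct: the free-text row has space for a number of visits, and respondents are asked to answer everything. That unprompted reporting will be less complete than a named row is a judgement, not something the documents show.

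**Conclusion.** The plan promises medication data at baseline, three months and follow-up, and nothing it shows or names collects them. Followed as written, the cost per patient and cost-utility results under Primary Outcomes would omit a stated component. This should be fixed before data collection. Confidence is good for the forms and schedule that can be read, and is tempered by those that are not reproduced.

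Three stronger readings are not supported.

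- A reader might infer that the between-arm cost per QALY is biased. The documents give no medication use or unit costs, so neither size nor direction can be derived, and the effect is nil if medication costs are equal between arms.
- A reader might infer that maintenance class contacts are excluded from costing. They are not; they depend on the participant entering them as free text. The class point is held at moderate confidence.
- A reader might infer that thin class counts undermine the question of whether community networks can take on the maintenance clinic's work. That item is in the Background and not among the Objectives, and NHS class attendance does not measure community capacity.

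The conclusion assumes that no further resource-use form exists outside the lists and the Table of Events. If one does, it must be scheduled.

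**What to change.** 1. State in Analysis of Outcomes that the appended Healthcare Usage Questionnaire is the modified CSRI or, if it is not, append the CSRI and add it to the questionnaire lists and the Table of Events.
2. Add a medication item (name and quantity, last 3 months) at baseline and each follow-up, or name a records source extracted in the same way for both arms.
3. If neither is feasible, remove medication from the stated costs and report the cost results as excluding it.
4. Smaller point: add a row to question 1 for the maintenance exercise class with the number attended, or take attendance from the service register for both arms.

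The cost is a form amendment. The downside is a slightly longer questionnaire with more to recall at each visit, or a records or register extract for all participants. Option 3 needs only a change of wording, but gives up a cost component the plan currently claims.
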